6.2 Investigational device and comparator

a) Exposure to the investigational device or comparator

Participants allocated to the intervention group will be provided with access to the program *alivis*, which is to be used additionally to the care provided by their attending practitioner. The program can be used on conventional web-browsers on desktop PCs, tablets and smartphones. Users (patients randomized to the intervention group) receive access to the program for 12 months by 12-digit personal codes (vouchers), provided by the developer. After initial registration and consent to the general terms and conditions, users can log into the program using their email address and personal password at any time. The program is set up as an adaptive- and responsive-web-design pulling a layout template for a specific device, adapting to dimension and resolution of the display used. This results in high flexibility of usage regardless of the available hardware.

An essential element of the program is the presentation of content through simulated dialogues, which are performed by interaction of the user with the software acting as a virtual expert. Users navigate through the modules by reading short texts and reacting to the information by continuously choosing one or multiple predefined options of response. Based on this input, the program subsequently adjusts the content. In this process, preferences and needs of the user are matched with regard to content and style. Brief text passages are accompanied by illustrations, audio recordings, worksheets and personalized summaries (pdf documents). Chats are presented in consecutive order and build on previous content. Moreover, optional daily short text messages (SMS) are sent as reminders aimed to motivate and support users in their daily lives. The program also offers a symptom tracking function; that is, users are invited to complete embedded questionnaires at regular intervals in order to self-monitor changes over time. Text and graphical feedback are provided automatically after users complete the questionnaires embedded in the program. Exercises that the user experiences as useful can be saved in a toolbox and practiced again in a 'practice corner'. A crisis module specifically aims at supporting users during difficult situations in daily life.

alivis is provided in addition to the care provided by the participants' attending practitioner (TAU). This may comprise any kind of treatment prescribed or recommended by a healthcare professional, including (but not limited to) pharmacotherapy, rehabilitation, psychotherapy, etc., as well as no treatment at all.

Participants in the control condition receive access to only TAU. After 12 months (T3), they have the option to receive access to *alivis*.

b) Other medical devices or medication

Not applicable.

c) Number of investigational devices

No additional investigational device (in addition to *alivis*) will be used in this trial.

6.3 Subjects

a) Inclusion criteria

- male, female, non-binary
- age 18-65
- diagnosis of BPD (telephone interview via SCID-5-PD (45))
- borderline severity score (cut-off) of ≥ 1.07 on the BSL-23
- Stable treatment (e.g., psychotherapy, medication, no treatment,---) for at least 30 days at the time of inclusion
- consent to emergency plan for suicidal crises
- consent to participation
- sufficient knowledge of the German language

b) Exclusion criteria

- Plans to change ~~in~~-treatment (e.g., psychotherapy, medication,---) in the upcoming 3 months after inclusion
- Comorbid diagnosis of substance use disorder
- Lifetime diagnosis of psychotic disorder like schizophrenia or schizoaffective disorder (except non-transitory paranoid ideas that can be concomitant with BPS and in which the ability to test reality is mostly preserved)
- Diagnosis of a physical condition that can cause serious psychiatric symptoms
- Acute decompensation of mental health symptoms, e.g. acute manic state or acute suicidality
- BMI <15
- current psychiatric day-care or inpatient treatment
- Prior use of *priovi*

c) Criteria and procedures for subject withdrawal or lost to follow-up

1) Withdrawal of a subject or stop of use

Participants will be informed of their right to withdraw from the study at any time without negative consequences. Test subjects will not be included in the clinical trial (not randomized) if it was not possible to ascertain baseline variables (T0). There is no provision for withdrawal of follow-up examinations.

2) Tracing of subjects lost to follow-up

At prespecified points in the course of the study, participants whose response to a survey is still outstanding will be reminded by email and/or phone.

Subsequent replacement of test subjects who evade follow-up examinations is not intended. Missing data points will be imputed by applying multiple imputation (cf. section 7. m). Possible reasons for being lost to follow-up include but are not limited to no further need for a treatment (known as “good enough effect” (57,58)), lack of positive effects of the treatment, or loss of interest among control group participants.

3) Replacement of subjects

Following standards for RCTs there will be no replacement of participants.

d) Point of enrolment

With randomization and allocation to a study group the participants are enrolled in the trial.

e) Point of randomization

After informed consent is obtained, patients interested in participation will be asked to fill in an online demographic questionnaire followed by a set of questionnaires to collect baseline data (T0). After initial data acquisition and screening for inclusion criteria, patients will be asked to take part in an initial telephone interview to conduct and determine the diagnosis of BPD, rule out any primary diagnosis of substance use disorder or psychotic disorder or acute decompensation of mental health, and to obtain consent to the emergency plan for suicidal crises. In case of a positive screening process regarding inclusion and exclusion criteria, participants will be allocated to a study group by randomization procedure. For further information regarding point of time see Table 1.

f) Total expected duration

Expected total duration of the entire study including recruitment is estimated as 24 months.

g) Expected duration for each subject

Expected total duration of the study for each participant will be up to 14 months (up to 1 month pre-assessment, 12 months intervention and follow-up phase, up to 1 month reminders for the last assessment).

h) Number of subjects

N = 470

i) Enrolment period

The enrollment period is estimated as ten months.

j) Relationship of investigation population to target population

The pragmatic RCT design, which evaluates the intervention in a setting in which it is also to be used, and the small number of exclusion criteria ensure that the test population largely corresponds to the target population of *alivis*. In addition, the required initial clinical interview contributes to the fact that *alivis* is only tested in the intended target group.

k) Vulnerable, pregnant, and breastfeeding population

Pregnancy or breastfeeding are no contraindications for the use of *alivis*.

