To date, a couple of digital health applications for BPD exist, which focus on tools from ST or from DBT (11,12). *alivis* is based primarily on DBT, which is the best-evaluated behavioral treatment method for BPD (5,13). DBT is a modular treatment program, and *alivis* makes use of several of these modules: for example, skills in emotion regulation, distress tolerance, antidissociative techniques, interpersonal effectiveness, and mindfulness are taught. These DBT modules are expanded in *alivis* to include modules on basic needs from ST (14,15), which has a good evidence base in BPD (13,16,17), on values work and defusion techniques from Acceptance and Commitment Therapy (ACT; 18–20) as well as on fostering self-compassion from Mindfulness Self-Compassion Therapy (MSC; 21) adapted to the needs of patients with BPD. Similar techniques have been integrated into more recent DBT protocols (22,23). The composition of the techniques used in *alivis* is thus based on the latest findings in psychotherapy research as well as on the extensive clinical expertise of the development team. Providing such a wide range of strategies enhances the chances that the patient will be able to make use of what they are offered and eventually profit from the intervention. *alivis* was developed by clinicians and researchers with long-standing expertise in the field of BPD which they have incorporated into the development of *alivis*, and with the involvement of patients suffering from BPD.

The aim of the present RCT is to examine the effectiveness of *alivis*, a self-guided digital intervention for BPD, to decrease symptom severity in BPD patients.

2. Identification and description of the investigational device

a) Summary description

Participants allocated to the intervention group will be provided with access to the program *alivis*. *alivis* is a CE-labeled, interactive online program for patients with BPD. *alivis* is organized in simulated dialogues that enable the patient to learn more about their disease and practice relevant skills and competences for managing their symptoms and improving their quality of life.

alivis is a class I medical device according to MDR 2017/745, Annex VIII, Chapter III with software safety class A according to IEC 62304.

b) Manufacturer

alivis was developed by GAIA AG, an e-health company in Hamburg, Germany, specialized on research and development of digital therapeutics.

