The application of *alivis* does not require training or any prior experience with the program.

i) Medical or surgical procedures involved in the use of the investigational device

Not applicable.

j) References to the Investigator's brochure (IB) and IFU.

Not applicable.

3. Justification for the design of the clinical investigation

a) evaluation of pre-clinical testing/assessment and prior clinical investigations

The ~~device~~ *alivis* safety and performance of *alivis* was evaluated and confirmed in ~~pilot evaluations~~ according to the requirements applicable to the ~~processes~~ of development of medical devices (IEC 62366, ISO 13485; MDR Annex I) ~~including class I medical devices~~ in a summative evaluation. This includes the verification of the functionality and content of *alivis* as well as evaluation of extensive clinical data from post-market surveillance of the technically equivalent devices *priovi* and *deprexis*. Clinical data from post-market clinical follow-up RCTs is available for the equivalent class I medical device *priovi*.

b) Clinical data relevant to the proposed clinical investigation

Several effective psychotherapeutic approaches for BPD exist (5,6). Previously published studies demonstrated initial promising effects of digital interventions for BPD (12), but so far, these digital interventions focused on isolated psychotherapeutic approaches (i.e., only ST (24) or only DBT (25)) or on psychoeducation (26). *alivis* represents modern psychotherapy for BPD by combining strategies from DBT, ST, ACT, and MSC supplemented with psychoeducation, and thus offers the patient a considerably wider spectrum of therapeutic offers than previous digital interventions for BPD. The developers of *alivis* are clinicians and researchers with long-standing expertise in the field of BPD which they have incorporated into the development of *alivis*.

c) Clinical development stage

Post-Market-Stage

Due to the CE-label of *alivis*, the trial will be a post-market clinical follow-up study in line with the existing intended purpose.

4. Benefits and risks

a) Anticipated clinical benefits

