6.1 General

This study is a pragmatic, prospective RCT with two arms (30). As *alivis* already holds a CE-marking, this trial will be a post-market clinical follow-up study in line with the existing intended purpose. The trial will include a control group which receives TAU ~~in addition to publicly available information material on BPD (Links to <https://borderline-info.de/> and <https://www.borderline-netzwerk.info/>),~~ and an intervention group which receives *alivis* in addition to TAU. The effectiveness of *alivis* will be tested by comparing the effects between both groups at three months (T1; primary hypothesis). Although participants will have access to *alivis* for 12 months in total, the relevant content of the intervention should be already covered after three months, with the remaining time mainly serving as refreshers and for stabilization (27). Therefore, we already expect effects to be present after three months.

Recruitment of patients will be conducted via online advertisement (e.g., Google Ads campaigns). Participants will be routed to a linked study website providing information about the trial and details about participation. Using a contact form on the website, participants will be able to indicate interest in participation whereupon they will receive an email with a link to LimeSurvey, a secure online survey tool. At the beginning of the survey, further information about participation will be provided and electronic informed consent will be obtained. Participants will be informed about the option to receive personal explanation and answers to further questions via telephone or email. Moreover, participants will be informed of their right to withdraw from the study at any time without negative consequences.

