~~Severity of borderline symptoms at T1, assessed via the Borderline Personality Disorder Checklist (BPD-CL).~~

~~The BPD-CL is a DSM-IV based self-report instrument to assess BPD symptoms in the previous month (42). Importantly, in contrast to the BSL-23, the BPD-CL explicitly assesses all nine DSM-5 criteria.~~

Patient activation at T1, assessed via the Patient Activation Measure (PAM-13)

The PAM13 assesses patients' active participation in their medical care using 13 items (43,44). Items are answered using a Likert scale ranging from 1 = "strongly disagree" to 4 = "agree strongly", yielding a total score between 13 and 52. The German version of the PAM13, the PAM13-G, is validated and demonstrates good psychometric properties, including a good internal consistency of Cronbach's $\alpha = 0.84$ (44). An improvement of 4 points on the PAM-13 is considered an MCID (56). Therefore, responders will be defined as patients who improve by at least 4 points on the PAM-13 from T0 to T2. The proportion of responders between groups will be compared using χ^2 tests.

~~The PAM-13 is a 13-item instrument assessing patients' active participation in their medical care (43). The German version of the PAM-13, the PAM-13-G, is validated and demonstrates good psychometric properties (44).~~

Exploratory Endpoints: Assessments listed in "Secondary endpoints" at T2/T3

Sociodemographic Variables:

- Age
- Gender

- Sex
- Education
- Employment Status
- Family Situation
- Language ability
- Ethnicity

Clinical Variables:

Assessed at T0 only:

- First diagnosis (date)
- Inclusion diagnosis (BPD) using the respective section of the SCID-5-PD interview (45)
- Psychiatric comorbidities (via Mini-DIPS) (46)
- Psychotherapy (past, type)

Assessed at all timepoints (T0-T3):

- Medications (name of medication, dose, frequency)
- Psychotherapy (current, type)
- Childhood trauma (via Childhood Trauma Questionnaire (CTQ; 47,48))
- Number of BPD-related hospitalizations (T0: past 12 months, T1-T2: past 3 months, T3: past 6 months)
- Number of hospitalizations due to other reasons (T0: past 12 months, T1-T2: past 3 months, T3: past 6 months)
- Number of days in sick leave (past 3 months)
- Number of days in sick pay (past 3 months)
- weight and height (current)
- Use of any other online program for BPD (T0: lifetime, T1-T2: past 3 months, T3: past 6 months; name)

Treatment satisfaction:

- Program Evaluation of the Program (NPS, Net Promoter Score) (49)

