The PAM13 assesses patients' active participation in their medical care using 13 items (43,44). Items are answered using a Likert scale ranging from 1 = "strongly disagree" to 4 = "agree strongly", yielding a total score between 13 and 52. The German version of the PAM13, the PAM13-G, is validated and demonstrates good psychometric properties, including a good internal consistency of Cronbach's $\alpha = 0.84$ (44). An improvement of 4 points on the PAM-13 is considered an MCID (56). Therefore, responders will be defined as patients who improve by at least 4 points on the PAM-13 from T0 to T2. The proportion of responders between groups will be compared using χ^2 tests.

Table 1| Chronological Sequence of the Trial

	Recruitment	Allocation	Post Allocation	Follow-up
Timepoint	T0		T1	T2, T3
Screening				
Test of Inclusion Criteria	x			
Test of Exclusion Criteria	x			
Sociodemographic Variables	x			
Clinical Variables	x		x	x
Consent	x			
Randomization		x		
Intervention				
Intervention group: alivis + TAU		♦	♦	♦
Control group: TAU + publicly available information material on BPD				
Endpoints				
BPD symptom severity (BSL-23)	x		x	x
Depression (PHQ-9)	x		x	x
General Anxiety (GAD-7)	x		x	x
Costs questionnaire	x		x	x
Social Functioning (WSAS)	x		x	x

Health-Related Quality of life (AQoL-8D)	x	x	x
BPD symptom severity (BPD-GL)	*	*	*
Patient activation (PAM-13)	x	x	x
Clinical Course	x	x	x
Net Promoter Score (NPS)*		x	x
Subjective improvement		x	x
Usage of the Program*		x	x
Exploratory Variables	x	x	x
Adverse Events (incl. NEQ)		x	x

T0: Before start of Intervention (baseline), T1: 3 months post allocation, Follow-up: T2: 6 months post allocation, T3 = 12 months post allocation. Black diamonds indicate access to *alivis*. *only assessed in the intervention group.

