Moreover, responder analyses will be conducted. Unless a specific MCID is specified for an endpoint in section 6.1d), responders will be defined by reaching the cut-off of 15% of the range of the scale (64). ~~the reliable change index (RCI; 33) will be used to identify responders to treatment in patients with complete observations. The RCI is calculated as the ratio of the difference between pre- and post-scores of an individual participant (numerator) and the standard error of measurement of the difference (denominator). RCI scores larger than 1.96 indicate that it is unlikely that the posttest score is not reflecting real change ($p < .05$), thus indicating that the participant is a responder (33).~~ If a specific MCID is specified for an endpoint, responder analyses will instead be based on that value. Responders will then be defined as participants reaching this difference from T0 to T1. Additionally, exploratory responder analyses will be conducted for each endpoint, where response is defined as 50% improvement since baseline. The proportion of responders between groups will be compared using χ^2 tests. Moreover, the odds ratio will be reported.

d) Significance level and power

significance level (α) = 0.05 (two-sided)
power = 0.80

e) Sample size

1) Clinical data on outcome variable and effect size

An effect of Cohen's $d = 0.27$ has been observed for a digital intervention for BPD that is based on ST only (27). Given that *alivis* consists of a combination of DBT, ST, ACT, and MSC and that participants will be closely guided during the trial, we expect the observed effect to be slightly larger and assume an effect size of $d = 0.30$. In order to obtain a power of 0.80, at a two-sided significance level of 0.05, each group should have a sample size of 176. Outpatient RCTs for BPD have an average dropout rate of approximately 25% (28,29). To compensate for dropouts, we thus aim to include and randomize $N = 470$ (2×235) participants with an allocation ratio of 1:1.

2) Expected outcomes across treatment groups

See 5. d.

3) Adjustments due to pre-planned interim analyses

An interim analysis is planned after three months (T1; primary time point). There will be no adjustments.

4) Effect size and non-inferiority margin

See 7. e 1).

5) Randomization allocation ratio

1:1, in variable blocks of 4, 8, or 16 participants each ~~no block randomization, no stratification~~

6) Expected drop-out rate

25% (28,29).

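### The prior-exposure exclusion covers priovi but neither alivis nor an earlier randomisation in this trial, and no exposure or per-protocol rule clearly covers alivis use by a control participant

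*Combined protocol and SAP*

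**What the plan says.** The only earlier program barred in Section 6.3 b) is priovi: "Prior use of *priovi". The synopsis (Section 1.4) and the pre-screen before the telephone interview (Section 6.4 a)) carry the same restriction and go no further. Section 3 a) describes priovi as an equivalent device.

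On the status of alivis, Section 3 c) states: "Due to the CE-label of *alivis*, the trial will be a post-market clinical follow-up study". Section 1.5 says the program was developed "with the involvement of patients suffering from BPD". Sections 2 g) and 6.2 a) say that trial users get in with a personal voucher code issued by the developer.

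Exposure during the trial is recorded through one item in Section 6.1 c): "Use of any other online program for BPD (T0: lifetime, T1-T2: past 3 months, T3: past 6 months; name". Table 1 lists program usage with a footnote that it is "only assessed in the intervention group". The per-protocol filter in Sections 7 a) and 7 c) drops participants of either arm who report other digital interventions for BPD in the relevant follow-up period.

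Entry begins online (Section 6.1): "Using a contact form on the website, participants will be able to indicate interest in participation". Consent, the baseline survey, a diagnostic telephone interview and automatic 1:1 randomisation follow. Enrolment is expected to last ten months (Section 6.3 i)). Controls are to have TAU only and may receive alivis after 12 months (Section 6.2 a)).

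**The concern.** By excluding priovi users, the plan accepts that earlier digital treatment can blur the comparison. It then leaves out the one program whose prior use would blur it most directly. As the criteria stand, a person who has already worked with alivis is eligible. So is a control participant who registers again, who would have a 50% chance of immediate access under 1:1 allocation instead of a 12-month wait.

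The later steps do not close the gap. The exposure item and the per-protocol filter speak of other programs, which most naturally means programs other than alivis. The filter also looks only at the follow-up period, so an answer about lifetime use at T0 triggers nothing.

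What is at stake is the contrast of alivis plus TAU with TAU only at T1. A control participant who uses alivis, or a prior user in either arm who has little left to gain, pulls the difference towards zero. A person randomised twice supplies two dependent records, possibly one in each arm, and the ANCOVA treats them as independent.

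**Working it through.** **The rules side by side**

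| Step | Prior priovi | Prior alivis | Already randomised |
|---|---|---|---|
| Exclusion list, 6.3 b) | barred | not mentioned | not mentioned |
| Synopsis, 1.4 | barred | not mentioned | not mentioned |
| Pre-screen, 6.4 a) | barred | not mentioned | not mentioned |
| Exposure item T0–T3, 6.1 c) | covered as another program | not clearly covered | not covered |
| Per-protocol filter, 7 a) and 7 c) | covered if used in follow-up | not clearly covered | not covered |

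**The plan's own sample size.** The inputs are "significance level (α) = 0.05 (two-sided" and power 0.80 (Section 7 d)), d = 0.30, 176 per group and 25% dropout (Section 7 e)).

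- Normal approximation: n = 2 × (1.96 + 0.8416)² / 0.30² = 174.4, so 175 per arm.
- Two-sample t-test: 175.4, so 176 per arm, which is the plan's figure.
- Dropout: 176 / 0.75 = 234.7, so 235 per arm and 470 in total, as stated.

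The sample size reproduces, and this point does not dispute it.

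**Sensitivity to exposure.** Let c be the share of the TAU arm that shows the full alivis effect. The documents give no value, so every c below is an assumption. The expected standardised difference becomes 0.30 × (1 − c), with the SD held fixed. The same expression applies if a share c of both arms are prior users who gain nothing further. Power is approximately Φ(0.30 × (1 − c) × √(176/2) − 1.96), with √(176/2) = 9.381.

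| c (assumed) | About how many of 235 controls | Effective d | Power, normal | Power, t-test |
|---|---|---|---|---|
| 0 | 0 | 0.300 | 0.804 | 0.801 |
| 2% | 5 | 0.294 | 0.788 | 0.785 |
| 5% | 12 | 0.285 | 0.762 | 0.760 |
| 10% | 24 | 0.270 | 0.717 | 0.714 |

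At a given c these are the largest losses, because each exposed control is credited with the whole effect. A partial effect in controls, or some further gain among prior users in the alivis arm, would make the loss smaller. The 10% row only shows how the formula behaves; nothing in the documents points to a share of that size.

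**The case against.** The strongest reply is that exposure outside the trial is not shown. A CE mark and post-market status are regulatory facts; no section says that alivis was sold, prescribed or distributed. Access needs a code from the developer. The clinical data cited in Section 3 a) come from priovi and deprexis, which fits a product with few or no outside users. Patient involvement in development is reported without numbers, and without saying that those patients used the finished program. All of this stands, and it means the size cannot be put above zero from the documents.

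A reader might also infer that exposed participants would go unnoticed and that the data could never reveal them. The documents do not support that. The T0 item covers lifetime use and asks for the program's name, and the T1 item covers the three months that matter for the primary endpoint, so a respondent could name alivis. The study manager holds names and contact data (Section 8 d)), and the developer issues the codes. What is missing is a described use of these resources and a rule that acts on the answer.

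Repeat enrolment is harder than a web form suggests. It requires a full baseline survey, a telephone diagnostic interview and a jointly written emergency plan. Monitoring (Section 6.5) looks at participant flow and at correct use of the criteria, but it cannot enforce a criterion that is not written.

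Finally, prior users fall into both arms by chance, so the bias they cause runs towards zero. Those who improved most may no longer reach the BSL-23 entry cut-off of 1.07. The primary analysis is ITT under a treatment-policy estimand (Section 7 r)), and the per-protocol analysis is exploratory. These points limit the consequence. They do not supply the missing criterion.

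**Conclusion.** The gap in the text is real. Three places bar priovi and none bars alivis or a second randomisation. Alivis use by a control participant is not systematically captured, and no eligibility or per-protocol rule clearly acts on it if it is reported.

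Its practical size is unknown and may be near zero. The power figures (80% falling to about 79% at an assumed 2% and 76% at an assumed 5%) are upper bounds for those shares, not predictions. They rest on the full effect in every exposed control, a fixed SD and the planned 176 analysable per arm. There is no evidence of contamination or of duplicate participants, and prior use by itself carries no expected bias in favour of alivis. This is a cheap improvement of minor severity.

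**What to change.** 1. In Section 6.3 b), the synopsis and the pre-screen in Section 6.4 a), replace the criterion with: 'Prior or current use of priovi or alivis, or previous randomisation in this trial'. Ask about it in the T0 survey.
2. Before randomising, check name and contact data against the participants already randomised. This can be done at the existing telephone interview.
3. Word the T0–T3 exposure item, for both arms, to include alivis obtained outside the study allocation.
4. In Sections 7 a) and 7 c), exclude control participants who report alivis use in the relevant period from the exploratory per-protocol set. Leave the ITT analysis unchanged.

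The cost is one eligibility line, one reworded item, one look-up and one clause, handled as an amendment under Section 9, plus perhaps a few more screen failures. N stays at 470, and no endpoint or primary analysis changes. If recruitment is already under way, items 2 to 4 can still be introduced for the remaining participants and visits and fixed before analysis.
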